We plan to enroll subjects with Severe Asthma (*Severe Asthma—American Thoracic Society Statement (51)*). Subjects will be recruited primarily from the PI's subspecialty UCAN™ asthma clinic. Severe asthma subjects must have at least 1 major and 2 minor criteria. Major criteria are 1) Requirement for treatment with high-dose ICS (>800mcg fluticasone or equivalent) and 2) Treatment with oral steroids >50% of year. Minor criteria are 1) Requirement for additional daily treatment with other controller medication (LABA, theophylline, LTRA, e.g.), 2) Asthma symptoms requiring SABA on daily basis, 3) Persistent airway obstruction (FEV1<80%, PEFr>20%), 3) 1 or more urgent care visits/year, 4) 3 or more oral steroid bursts/year, 5) Near-fatal asthma event in past.

2. Address how subjects will be recruited: XXX direct person to person solicitation, ___by telephone, ___letter, ___advertisement, ___press release, notices, ___other. Provide the text.

Study locations and Subject Characteristics:

The Sacramento community has a large degree of ethnic diversity; approximately 10% are of African American ancestry, 10% Asian and 20% Hispanic. This is reflected in our UC Davis Pulmonary clinics and our Severe Asthma/ UCAN™ clinic. Our community has always been very responsive to our recruitments. The study locations will be the existing UC Davis Pulmonary clinics that house the UCAN clinics, the UC Davis CTSC Clinical Research Center that is also located in the VA Mather Hospital, The UCAN clinic is affiliated with the University of California, Davis and is one of two specialized, chronic disease management clinics in the university. Two respiratory therapists (1 Certified Clinical Research Coordinator) have 100% appointments in this clinic to assist in the treatment of referred patients with severe asthma.

3. State from where subjects will be recruited, when and how many.

Study locations and Subject Characteristics:

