The study locations will be the existing UC Davis Pulmonary clinics that house the UCAN clinics, the UC Davis CTSC Clinical Research Center that is also located in the VA Mather Hospital, the locations are: UC Davis Pulmonary clinics (including the UC Davis Asthma Network clinic) at [name]. One primary source of patients will be the UC Davis Asthma Network clinics (UCAN), where [name] serves as Co-Director. [name] and colleagues see many subjects with diagnosed severe asthma and many of these subjects will fit the criteria for enrollment in this study. We maintain a database of over 700 subjects treated by us in the past 10 years. The UCAN asthma clinic saw approximately 720 referred patients from 1999-2007. 77% of the referrals were women with a mean age of 46.3±15.3 (mean± SD) years. (Kivler et al JACI 2002, 109:S314, Kivler et al. AJRCCM 2003, 167:A209).

4. Specify the age of the research subjects.

Asthmatic patients aged 18-80 will be enrolled.

5. List all criteria for including and excluding subjects.

Inclusion and Exclusion Criteria: Inclusion a) Adult patients >18 years or older with ATS definition of severe asthma, b) History of recent exacerbations ≥ 2 in past 2 months) or Asthma Control Test score < 20/25. Subjects will meet this definition based on the use of high dose ICS and LABA use (Table 3) plus an even distribution among minor criteria 2-5. *Exclusion:* a) Less than 18 years of age; b) baseline FEV1 <30% predicted, c) pregnant or nursing women, e) current smokers or subject with >15 pack year history, f) any history of intolerance of, or reaction to, L-arginine.

Controller Medications for Study: Upon enrollment, all subjects will be treated with high dose ICS and LABAs throughout the 8-month period. The overwhelming majority of the UCAN™ patients are on one of these two ICS. In addition, all subjects will be on scheduled LABAs, and will be aware of the FDA Black Box warning on these medications. Additional controller medication including leukotriene inhibitors will not be stopped, and it is expected that the use of these other medications will be roughly equal between the two groups.

6. If women and minorities are excluded, provide rationale for such exclusion.

Women and minorities will not be excluded. Many enrolled subjects will be women as severe asthma in adults is approximately 60-70% women.

SPECIAL/VULNERABLE POPULATION (if applicable):

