The primary endpoint was the total number of "moderate" exacerbations during the 12-week interventional period, as defined by recent the ATS/ERS 2009 statement [2]. A moderate asthma exacerbation is defined as any of the following: 1) a drop in am PEF>30% from baseline on two consecutive days, 2) need for initiation of oral steroids or an increased dose of inhaled corticoid steroid on any two consecutive days, 3) doubling of short-acting β -agonist use (e.g. number of puffs of albuterol)/ day for 2 consecutive days [3-5]. The secondary clinical endpoints were recorded at each of the six study visits, these included: 1) asthma control test score, 2) FEV1 (liters), 3) FVC (liters), 4) FEV1/FVC (%), and 5) Weight. The secondary biological endpoints including FeNO and untargeted metabolites.

Metabolites measurement

Longitudinal plasma metabolite levels were measured by hydrophilic interaction liquid chromatography (HILIC) in both positive and negative modes and gas chromatography (GC) mode. The peak intensity was measured for the compounds and were annotated to specific known metabolites. Relative standard deviation (RSD) for each compound found in more than one mode in quality control samples were calculated and the intensities of compound with lowest RSD was chosen for the downstream analysis.

Clinical trial analysis

For the sample size calculation, we used a conservative power estimate based on t-test analysis of 2x2 cross-over design [6]. For a sample size of 50 people, we would have 95% power to detect a 0.6 standard deviation change in the mean lung function at $\alpha = 0.025$ and accounting for 10% attrition rate. Improvements of this magnitude are consistent with those reported in recent crossover trials in asthma with either FEV1 [7], symptoms scores [8], or AM PEF [9] as outcomes. Statistical analyses for the clinical trials were performed using SAS University Edition (SAS Institute Inc., Cary, NC, USA.) and R (public access). Data were analyzed on an intention-to-treat basis and the significant level was defined by p value less than 0.05. A generalized linear mixed model was used for analysis accounting for correlated repeated measurements which enable us to account for expected missing data points [10]. This model considered differences in baseline levels of function, by allowing for person-specific random effects (random intercepts). The distribution of exacerbation events was assumed to be a Poisson distribution. For

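### The primary endpoint counts starting oral steroids but not raising an existing oral dose, so some flares in eligible maintenance users can go uncounted

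*Combined protocol and SAP*

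**What the plan says.** The primary endpoint is the number of moderate exacerbations in a 12-week treatment period (SAP, Outcomes). Any one of three criteria is enough: "A moderate asthma exacerbation is defined as any of the following".

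- Criterion 1: "a drop in am PEF>30% from baseline on two consecutive days".
- Criterion 2: "need for initiation of oral steroids or an increased dose of inhaled corticoid steroid on any two consecutive days".
- Criterion 3: "doubling of short-acting" beta-agonist use, for two consecutive days.

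On eligibility, Subject Selection item 1 states: "Severe asthma subjects must have at least 1 major and 2 minor criteria". One of the two major criteria is "Treatment with oral steroids >50% of year"; the other is a requirement for high-dose inhaled corticosteroid (ICS). The exclusions in item 5 do not mention oral steroid use. Item 5 also describes how subjects are expected to qualify: "Subjects will meet this definition based on the use of high dose ICS and LABA use (Table 3) plus an even distribution among minor criteria" (numbers 2 to 5). Under Controller Medications for Study, "all subjects will be treated with high dose ICS and LABAs throughout the 8-month period".

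No passage says how a change in an existing oral steroid dose is scored.

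**The concern.** Criterion 2 treats the two steroid routes differently. For inhaled steroid, a higher dose counts. For oral steroid, only a start counts. A subject who takes oral steroids every day cannot start them, so a flare managed solely by a higher oral dose fails criterion 2 as written. A scorer might instead treat a burst on top of maintenance as a start; no rule settles this, so similar flares could be scored differently.

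The other routes may catch such a flare, but nothing in the documents shows that they will. All subjects are on high-dose ICS, which may leave limited room for an inhaled increase. Daily rescue use is itself a minor entry criterion, so a doubling may have to start from a high base. The peak-flow route needs a fall of more than 30% on two consecutive days.

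At stake is the sensitivity of the primary count in a group that the protocol expressly admits.

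**Working it through.** **Plan's own figure.** The only power figure is 95% for a 0.6 SD change in mean lung function (SAP, Clinical trial analysis). It reproduces: 50 × 0.9 = 45 completers, noncentrality 0.6 × √45, two-sided alpha 0.025, SD read as that of the within-subject difference, gives 95.2%. It uses no exacerbation rate, so it neither supports nor contradicts this point.

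**Which flares are lost.** Take a subject on maintenance oral steroids whose flare is treated by raising the oral dose.

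| Also present | Counted? |
|---|---|
| Morning peak flow down more than 30% on two days | Yes, criterion 1 |
| Inhaled steroid dose raised on two days | Yes, criterion 2 |
| Rescue use doubled for two days | Yes, criterion 3 |
| None of these | No |

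**Effect on the treatment estimate.** The SAP fits a Poisson mixed model with person-specific intercepts. Let subject i have underlying rate λ_i, treatment rate ratio R and miss rate m_i.

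- Expected counted events on placebo: λ_i(1 − m_i).
- Expected counted events on L-arginine: λ_i·R·(1 − m_i).
- Ratio: R.

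With m_i equal in both periods, (1 − m_i) goes into the intercept. The within-subject rate ratio is unchanged and, on the log scale, so is the treatment-by-FeNO interaction. What falls is the number of events.

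**Size, on assumed inputs.** Let p be the share of all events that arise in maintenance users and q the share of those that meet no other route. The documents give neither.

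- Share of events lost: L = p × q.
- The variance of the log rate ratio is 1/E₁ + 1/E₂, where E₁ and E₂ are the expected counts on placebo and L-arginine. Both scale by (1 − L), so the standard error is multiplied by 1/√(1 − L).
- Low end: 0.10 × 0.25 = 2.5% lost; 1/√0.975 = 1.013.
- High end: 0.30 × 0.75 = 22.5% lost; 1/√0.775 = 1.136.

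Here p is a share of events. It equals the share of subjects only if maintenance users have the same event rate as the rest.

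**Illustrative power.** Assumptions: 45 completers, rate ratio 0.67 (borrowed from the 33% responder threshold), two-sided alpha 0.05, Wald test on the log rate ratio. The placebo event rates are assumed.

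| Placebo events per subject per 12 weeks | No loss | 2.5% lost | 22.5% lost |
|---|---|---|---|
| 1 | 39.8% | 39.0% | 32.2% |
| 2 | 67.2% | 66.1% | 56.3% |
| 3 | 83.8% | 82.9% | 73.7% |

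For 2 events and no loss: E₁ = 90, E₂ = 60.3, standard error 0.166, and 0.400/0.166 − 1.96 = 0.45, hence 67.2%.

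**Responder rule.** The SAP defines response by a 33% reduction in individual events relative to placebo. A subject with 3 placebo and 2 L-arginine events has (2 − 3)/3 = −33.3% and is a responder. If one placebo event is unscored, (2 − 2)/2 = 0 and the subject is a non-responder. A subject with a single placebo event, unscored, has a zero denominator and drops out, if the SAP's exclusion for zero events at baseline refers to that denominator.

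**The case against.** The strongest case against is that the gap is narrow.

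- **Only one route is restricted.** A reader might infer that the endpoint recognises oral steroid starts and nothing else, or that flares in maintenance users are missed as a rule. Neither follows. A flare is lost only when it meets no other route. The inhaled route is not closed either: item 1 of Subject Selection gives an ICS level to exceed, not a ceiling. This stands, and limits the claim to flares that can be missed.
- **The group may be small.** A reader might take near-continuous oral steroid use to be required at entry. It is one of two alternative major criteria, and item 5 expects subjects to qualify through ICS and LABA. More than half the year is also not continuous use: intermittent users, and those treated in bursts, can still start oral steroids. This stands, although a subject who qualifies through ICS may also take maintenance oral steroids.
- **No bias is shown.** A reader might infer a biased treatment effect. That would need a miss rate that differs between L-arginine and placebo, and nothing in the documents indicates one. Uneven maintenance use across FeNO groups would not by itself bias the interaction. It could distort a raw between-group count, which is one reading of Aim 1, but the SAP does not name that as its test and the documents do not say how maintenance use is distributed by FeNO group.
- **The source may cover it.** The definition is attributed to a cited society statement that cannot be checked here. A scorer working from the SAP would still apply the SAP's words.
- **It may be late.** The SAP is written in the past tense in a December 2019 update. This bears on the form of the fix, not on the gap.

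**Conclusion.** The point holds in a limited form. Scored as written, criterion 2 does not count a rise in an existing oral steroid dose, although subjects on such treatment are eligible. Some of their flares can therefore be left out of the primary count.

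The supported cost is fewer events and less precision, with possible misclassification in the responder analysis. The 2.5–22.5% event loss and 1–14% rise in standard error rest wholly on assumed values of p and q; at the low end the effect is negligible. The absence of bias in the within-subject effect rests on equal miss rates in the two periods. A claim that the primary result is biased, or that most flares in these subjects are lost, goes beyond the documents.

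**What to change.** For endpoint scoring only, extend criterion 2 so that it is met by any of the following on two consecutive days: a start of oral steroids, an increase above the stable maintenance oral dose, or a higher inhaled steroid dose. This changes how events are classified, not how subjects are treated.

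Tabulate baseline maintenance oral steroid use by FeNO group, so that readers can see how many subjects are affected and whether a raw group comparison is at risk.

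Set the rule before unblinding. If data have already been seen, keep the present definition as primary and report the revised scoring as a labelled sensitivity analysis.

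The cost is small extra coding work, on one condition: oral dose changes must be recoverable. The study outline lists a symptom and peak-flow diary and updated clinical histories but does not say that steroid doses are recorded in them. If they were not, report the number of maintenance users and state the limitation.

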Research subjects are encouraged to report any adverse effects to the PI, Co-PI or study personnel, who will suggest ways to minimize the problems. The PI and Co-PI will review all adverse events. The review may lead to the recommendation that the subject be withdrawn from the study. When appropriate, the subject will be referred to their primary physician. In accordance with NIH regulations, reportable adverse effects arising from any of the procedures will be submitted promptly to the UC Davis Office of Human Research Protection and the PI will be notified of any subsequent reporting by the UCD OHRP to the NIH. Although they are not anticipated to occur, Unanticipated (non-serious) or Serious Adverse Events will be reported to the IRB within 5 working days of awareness of the event. Copies of reports should be received by the IRB office no later than 15 calendar days after the event. In addition, adverse events in all categories will be included in the PIs annual reports to the IRB as required by the federal regulations. All subjects will be seen by the PI and co-investigators. Research

subjects are followed by their regular physicians, so they will continue to receive usual care. [name] and co-investigators will review safety parameters prior to enrollment. The PI reviews and reports on the progress of the study on a semi-annual basis. The PI will monitor study progress, outcomes and participant safety, and may make recommendations on changes to the study protocol. The PI will review safety on an ongoing basis. All reportable adverse events will be compiled, and reported in summary form, on an annual basis to the IRB, and at the conclusion of the study. Unanticipated adverse events and serious adverse events will be reported to the IRB. The protocol is reviewed annually by the IRB in conjunction with adverse event information.

ClinicalTrials.gov Requirements: Aims 1 will be reported on the clinicaltrials.gov website. We will register with ClinicalTrials.gov within 21 days after enrollment of the first patient. Summary result information will be reported within one year of completion of the trial.

5. If the study involves the use of placebo, justify why this is appropriate.

While this study includes a placebo, it is an -add-on placebo. Subjects will be on their standard asthma medication. This is part of the inclusion criteria for the study. This will be monitored at study visits.

BENEFITS:

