the primary hypothesis, we included an indicator in the model that allows for the subjects to be on active treatment. We first examined the carryover and period effect then tested for the treatment effect and examined the interaction term between treatment and FeNO. For secondary clinical outcomes, we performed the same analysis except we used linear mixed effect for the continuous endpoints.

Identify baseline metabolites as predictors for treatment response

We further defined the treatment response by reducing exacerbation events by 33% during L-arginine treatment. The individual event reduction was calculated by (events during treatment period minus events during placebo period)/events during placebo period. Subjects with zero event at baseline or did not complete both treatment and placebo phase were excluded. The baseline metabolomic profiling (first visit) was used for the downstream analysis. Partial Least Square-Discriminant analysis (PLS-DA) and hierarchical cluster analysis (using Euclidean as similarity measure and Ward's linkage as clustering algorithm) were performed using MetaboAnalyst 4.0 [11]. to identify the predictive metabolites. Clinical characteristics were compared between treatment response versus non-response groups using t-test (continuous characteristics) or Fisher's exact test (categorical characteristics with small sample sizes).

Longitudinal metabolomic profiling analysis

A linear mixed model was used to test the association between the longitudinal metabolite intensities and the clinical outcomes including FeNO at each visit. Metabolites pattern change between two biological conditions including 1) treatment vs. placebo, 2) high vs. low FeNO groups during treatment period, 3) treatment response vs. non-response groups during treatment period were tested using the method of multivariate empirical Bayes (MEBA) time-series analysis [12] built in the MetaboAnalyst 4.0. Hotelling-T2 statistics were used to rank the metabolites with different temporal profiles between two biological conditions under the study.

References

- [name], Last M., Bratt J.M., Kwan V.W., O'Roark E., Linderholm A. L-Arginine Supplementation and Metabolism in Asthma. *Pharmaceuticals* 2011, 4, 187-201.

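### The primary exacerbation count makes no allowance for time observed and has no rule for a period cut short, so unequal early leaving would bias the treatment comparison, in either direction

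*Combined protocol and SAP*

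**What the plan says.** Under Statistical Analysis Methods, Outcomes, the primary endpoint is the total of moderate "exacerbations during the 12-week interventional period". Under Clinical trial analysis, the model is a generalized linear mixed model with person-specific random intercepts, and "The distribution of exacerbation events was assumed to be a Poisson distribution". The population is set by "Data were analyzed on an intention-to-treat basis and the significant level was defined by p value less than 0.05". The named terms are an active-treatment indicator and those in this sentence: "We first examined the carryover and period effect then tested for the treatment effect and examined the interaction term between treatment and FeNO". No offset, person-time or event rate appears in the analysis text.

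On incomplete data there are two statements. The mixed model is described as "accounting for correlated repeated measurements which enable us to account for expected missing data points", and the sample size is given as "accounting for 10% attrition rate". Shortened participation is foreseen elsewhere too: under Plan for AE Reporting, "The review may lead to the recommendation that the subject be withdrawn from the study". Subjects who do not finish both phases are excluded from the responder analysis (section on baseline metabolites as predictors). The primary analysis has no corresponding rule.

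**The concern.** A raw count can be compared between treatments only if the time over which events could be counted is the same. The design plans 12 weeks on each treatment, so with full follow-up no exposure term is needed. With early leaving it is.

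Take a subject with one event who leaves at week 4. The rate is 3 per 12 weeks, but the record shows 1. A random intercept copes with a period that has no record at all. It cannot tell a 4-week count from a 12-week count, so the sentence about missing data points does not deal with this case.

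At stake are the treatment effect on the primary endpoint and, if leaving differs between FeNO groups, the treatment-by-FeNO term that carries the trial's hypothesis.

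**Working it through.** **The plan's own figure.** The SAP states 95% power for 50 subjects, a 0.6 SD change, alpha 0.025 and 10% attrition. With 50 × 0.9 = 45 completers, 43 degrees of freedom, noncentrality 0.6 × √45 = 4.02 and two-sided alpha 0.025, the power is 95.2%. The figure reproduces, taking 0.6 in units of the SD of the within-subject difference. It concerns lung function, so it neither supports nor weakens the count analysis.

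**Inputs.** From the documents: 50 subjects, a two-period cross-over with 12 weeks on each treatment, and 10% attrition overall. Not in the documents, and assumed:
- Event rate: 1.0 to 2.8 per 12 weeks. The upper end converts the entry criterion of 2 exacerbations in 2 months (2 × 84/60 = 2.8). Entry is also possible on symptom score alone, so a lower rate is plausible.
- Random-intercept SD: 0.7.
- Leaving times: uniform over the period.
- Split of leavers between treatments: varied.

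**Closed form, no true effect.** If a share d leaves on L-arginine after a mean fraction f of the period, the mean count there is λ[(1 − d) + d·f], against λ on placebo. The apparent rate ratio is therefore 1 − d(1 − f).
- d = 10%: 1 − 0.10 × 0.75 = 0.925 (f = 0.25); 1 − 0.10 × 0.50 = 0.950 (f = 0.50); 1 − 0.10 × 0.25 = 0.975 (f = 0.75).
- All 10% on placebo, f = 0.50: 1/0.950 = 1.053.
- Split 8%/2%, f = 0.50: 0.96/0.99 = 0.97. Split 6%/4%: 0.97/0.98 = 0.99. Split 5%/5%: 1.00.

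**Simulation.** There were 1,000 trials per row with true rate ratio 1.00. The Poisson random-intercept model had treatment and period terms, and a subject leaving in period 1 had no period 2 record. The last two columns give false positives favouring L-arginine (nominal 2.5%).

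| Leaving, L-arginine / placebo | Events per 12 weeks | RR, no offset | RR, offset | RR, cut-short period set to missing | False positives, no offset | False positives, offset |
|---|---|---|---|---|---|---|
| 10% / 0% | 1.0 | 0.953 | 0.993 | 0.992 | 4.0% | 2.8% |
| 10% / 0% | 2.8 | 0.967 | 1.002 | 1.001 | 4.9% | 1.9% |
| 0% / 10% | 2.8 | 1.031 | 0.996 | 0.995 | 2.8% | 3.8% |
| 5% / 5% | 1.0 | 1.012 | 1.012 | 1.013 | 2.3% | 2.1% |
| 5% / 5% | 2.8 | 1.003 | 1.002 | 1.002 | 2.5% | 2.5% |
| 20% / 0% (stress case) | 1.0 | 0.914 | 0.996 | 0.995 | 6.0% | 2.4% |
| 20% / 0% (stress case) | 2.8 | 0.930 | 1.002 | 1.002 | 7.8% | 1.9% |

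Monte Carlo error on rejection rates is about 0.7 percentage points. In the third row, false positives favouring placebo are 4.9% without the offset and 2.6% with it. Total rejection with the offset there is 6.4%, about two Monte Carlo standard errors above 5%. The 1.012 in the fourth row appears with and without the offset, so truncation does not cause it. A separate simulation under no true effect gave 0.97 (10%/0%), 0.93 (20%/0%), 1.04 (0%/10%) and 1.00 (5%/5%) without an offset, and 1.00 to 1.01 with one.

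**Size against sampling error.** With 50 events per treatment (1.0 per subject), the SE of the log rate ratio is roughly √(2/50) = 0.20, and ln 0.953 = −0.048 is a shift of 0.24 SE. With 140 events (2.8 per subject), the SE is roughly √(2/140) = 0.12, and ln 0.967 = −0.034 is a shift of 0.28 SE. The normal tail areas beyond −1.96 + 0.24 and −1.96 + 0.28 are 4.3% and 4.6%, in line with the simulated 4.0% and 4.9%.

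**The case against.** The strongest reply is that the plan never says a truncated count is entered as a full one. The endpoint is defined over 12 weeks and missing data points are expected, so a period short of 12 weeks might be set to missing. The table shows that this avoids most of the bias when leaving is unrelated to events. This stands as far as it goes: what the documents establish is an absent rule and an absent exposure term. But a total count under intention to treat most plainly means that the observed count is used. Setting such periods to missing also discards observed events, and can itself bias the result if leaving follows exacerbations.

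A reader might infer that the primary test is biased towards L-arginine, because the Risks section mentions cramping and bloating. The documents do not support that. The same section calls the risks of L-arginine minimal, and no split of attrition by treatment is given. If subjects leave because of exacerbations and L-arginine works, more would leave on placebo and the bias would run against L-arginine.

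The one-sided splits are also unfavourable cases, not forecasts. The 10% covers both periods and the washout, and an 8%/2% split already brings the ratio to 0.97 by the closed form. Placing all five expected leavers in one FeNO group of 25 on one treatment would be 20% one-sided leaving within that group, again an extreme. All of this limits the size of the point. It does not supply the missing rule.

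**Conclusion.** The point holds as a conditional one. The primary count analysis has no exposure term and no rule for a period cut short, while the plan expects attrition. On the plain reading, the treatment with more early leaving looks better, whichever it is.

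At the stated 10% attrition the apparent rate ratio under no effect is about 0.95 to 0.97 if all leaving is on L-arginine, with false positives in its favour of about 4% to 5% against 2.5%. It is about 1.03 to 1.04 if all leaving is on placebo, and about 1.00 if balanced. The one-sided shift is about a quarter of a standard error. If leaving is also early (a quarter of the period observed), the closed form reaches 0.925. The 20% one-sided results (0.91 to 0.93, about 6% to 8%) go beyond the stated attrition and serve only as a stress case.

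These sizes rest on the assumed event rate, between-subject spread, leaving pattern and split. The documents do not show that the trial's result is biased. The change should still be made, because the exposure term is standard, costs little, and leaves the treatment estimate alone when exposure is equal.

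**What to change.** 1. Add log(days observed in the period) as an offset to the Poisson mixed model and report the treatment effect as a rate ratio.
2. Define days observed as running from period start to the earlier of period end or the last diary or contact date.
3. State that every period with some follow-up enters with its own days, and that only a period with no follow-up is missing.
4. Report observed time and early leaving by treatment, period and FeNO group, so that a reader can see whether leaving was balanced.
5. Add a sensitivity analysis that fills the unobserved days of early leavers at the placebo rate. The offset assumes that the rate on observed days also applies to unobserved ones, so it does not fully correct leaving caused by exacerbations.

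The cost is one derived variable, some SAP wording and a slightly larger standard error for truncated periods. Sample size and conduct do not change. There are two practical limits. The protocol says that a symptom and peak flow diary is started, but does not say that a last diary or contact date is held as a data field, so this must be confirmed. The statistical section is written in the past tense; if the analysis has already been run, the model can be refitted wherever those dates exist, and should be labelled as a later addition.
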